7.3 Subject Population(s) for Analysis

Statistical analysis will be performed on: (i) intention-to-treat basis (i.e., inclusion of subjects randomly assigned, regardless of adherence, actual treatment received, and subsequent withdrawal of treatment

and/or deviation from the protocol); and (ii) per-protocol basis (i.e., inclusion of subjects who completed the treatment as planned).

8 Safety and Adverse Events

8.1 Adverse Event Definitions

The following are specific definitions of terms guided by the International Conference on Harmonization (ICH) Guidelines for Good Clinical Practice (GCP) and the U.S. Code of Federal Regulations that apply to this section:

Adverse Event: Any untoward medical occurrence in a subject or clinical investigation subject administered a pharmaceutical product and which does not necessarily have to have a causal relationship with this treatment. An AE is any unfavorable and unintended sign, symptom, or disease temporally associated with the use of an investigational medicinal product (IMP) or other protocol-imposed intervention, regardless of attribution. This includes the following:

- AEs not previously observed in the subject that emerge during the protocol-specified AE reporting period, including signs or symptoms associated with Dry Eye Disease (DED) that were not present prior to the AE reporting period.
- Complications that occur as a result of protocol-mandated interventions.
- If applicable, AEs that occur prior to assignment of study treatment associated with medication washout, no treatment run-in, or other protocol-mandated intervention.
- Preexisting medical conditions (other than the condition being studied) judged by the investigator to have worsened in severity or frequency or changed in character during the protocol-specified AE reporting period

Subjects will be reminded to inform the study staff of any adverse effects that they have experienced or are experiencing after the first administration of study drug. In addition, subjects will record adverse events in their diary throughout the study. All reports of adverse events during the study will be recorded on an Adverse Event Case Report Form (CRF). The subject should not be prompted about any adverse events that may occur during this trial.

All AEs and SAEs whether volunteered by the subject, discovered by study personnel during questioning, or detected through physical examination, laboratory test, or other means will be reported appropriately. For each adverse event, the following information will be recorded on the subject's Case Report Form(s): onset date, end date or continues, intensity, duration, relationship to test patch, action taken, and outcome. If a subject experiences a serious adverse event (SAE), study staff may discontinue the subject from study participation. The study staff must notify the IRB within 24 hours of receipt of the information. The study staff will instruct the subject to notify the research facility should any adverse event occur within 7 days of study completion. (For definitions of an AE and SAE, see below). Subjects who withdraw due to an adverse event may be replaced.

- **Serious Adverse Event:** An AE should be classified as an SAE if the following criteria are met:
 1. It results in death (i.e., the AE actually causes or leads to death.).
 2. It is life-threatening (i.e., the AE, in the view of the investigator, places the subject at immediate risk of death. It does not include an AE that, had it occurred in a more severe form, might have caused death.).
 3. It requires or prolongs inpatient hospitalization.
 4. It results in persistent or significant disability/incapacity (i.e., the AE results in substantial disruption of the subject's ability to conduct normal life functions).

5. It results in a congenital anomaly/ birth defect in a neonate/infant born to a mother exposed to the investigational medicinal product (IMP).
6. It is considered a significant medical event by the investigator based on medical judgement (e.g., my jeopardize the subject or may requires medical or surgical intervention to prevent any of the occurrences listed above.

To ensure consistency of AE and SAE causality assessments, the following general guideline will be applied:

Yes

There is a plausible temporal relationship between the onset of the AE and administration of the IVIG, and the AE cannot be readily explained by the subject's clinical state, intercurrent illness, or concomitant therapies; and/or the AE follows a known pattern of response to the IVIG; and/or the AE abates or resolves upon discontinuation of the IVIG or dose reduction and, if applicable, reappears upon re-challenge

No

Evidence exists that the AE has an etiology other than the IVIG (e.g., preexisting medical condition, underlying disease, intercurrent illness, or concomitant medication); and/or the AE has no plausible temporal relationship to IVIG administration (e.g., cancer diagnosed 2 days after first dose of study drug)

Life-threatening: Any adverse drug experience in which the subject was at risk of death at the time of the event. It does not refer to an event which hypothetically might have caused death if it were more severe.

Expected adverse event: Expected adverse events are those adverse events that are listed or characterized in the Package Insert (P.I) or current Investigator Brochure (I.B).

Unexpected adverse event: Any adverse event, the specificity or severity of which is not consistent with the current Investigator's Brochure.

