1.4 Dry Eye Disease: Clinical Signs and Symptoms

Common signs and symptoms of DED include: eye redness, ocular pain, burning and stinging sensation, foreign body sensation, pruritus, itchy or scratchy eye sensation, tired eyes, enhanced eye pressure, photophobia, painful mucous discharge, and in some cases epiphora. DED typically affects eyes bilaterally. Dry eye can heavily impact visual function especially during visually intensive activities and can overall decrease quality of life.^{4, 6} **Our clinical data shows that patients who have ACPAs in the tear fluid have more severe signs of DED (Table 1).**

Group	ACPA in tear fluid (units)	CCP in serum (units)	Signs			
			Schirmer I (median)	Corneal staining (median)	Conjunctival staining (median)	Corneal melts/scars (% eyes)
ACPA+/CCP+	148.0	160.0	1.0	5.0	4.0	25
ACPA+/CCP-	14.0	4.0	7.0	2.0	2.0	12.4
ACPA-/CCP-	-1.0	4.0	8.0	1.0	2.0	9.4
p value	<0.001	<0.001	<0.001	0.020	0.027	--

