3.5.2 Ophthalmic Examination

At all visits, the Investigator will conduct a complete undilated examination of the eyes using a binocular slit lamp. The Investigator will examine the tear film, eye lids, lashes, bulbar and palpebral conjunctiva, upper and lower lid puncta, cornea, anterior chamber, iris, lens, and anterior vitreous. Specific signs (if they are present) that will be recorded include: lacrimal sac area erythema, swelling or tenderness; froth or debris or mucous strands in tear film; eyelid hyperemia; punctal hyperemia or atresia; conjunctival/ episcleral hyperemia; papillary or follicular conjunctival reaction; chemosis, episcleral edema; superficial punctate keratopathy, corneal scar, corneal neovascularization; presence and

number of corneal filaments, presence or absence of mucoid films, anterior chamber cell, flare or KPs; pupil shape abnormalities, anterior or posterior synechiae, iris neovascularization; lenticular opacities; vitreous cells or pigment. Conjunctival hyperemia (ocular surface redness) will be graded at each visit using the VBR grading system as explained in section 3.4.5. Measurements at first and last visit will include: visual acuity (Snellen's chart), manifest refraction and intraocular pressure measurement. Clinically significant changes from baseline examination will be recorded on the adverse event forms. Corneal filaments are mucous tags that are adherent to the surface of cornea. Mucoid films are mucous collections accumulating on the surface of the eye. The number of such mucus tags/ filaments will be counted on each clinical examination (slit-lamp examination).

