Patients will be enrolled if they have been using their eye treatments for at least 30 day prior to the baseline visit and patients will be asked to commit to continue using the same treatments for the duration of the study. Participants will also be permitted to continue ancillary treatments such as eyelid massage or warm compresses of the eyelids. The number of drops and frequency must be recorded in the subject diary provided. The use of any investigational agent during past 30 days is prohibited.

The subjects will be monitored at 4 week intervals to ensure that they are not subjected to any undue risks during the course of the study. Additionally, they will be warned of the possible signs and symptoms of clinical worsening of DED, and advised to contact the research team immediately in case any of those symptoms occur. Subjects will also be encouraged to contact the research team in case they experience any ocular discomfort during the wash out period or during the course of the study. The subject's condition will be monitored by the physician (Principal Investigator) at each study visit, as well as at any interim visit (in case of adverse symptoms, as mentioned above). Any worsening of DED or any adverse event due to the study drug will be recorded. In case of clinical worsening, based on the individual subject's clinical condition, one or more of the following therapeutic decisions may be implemented: (1) Increasing/adding the use of artificial tears or ointments (2) Increasing/adding the use of anti-inflammatory therapy (Restasis/ Xiidra/ Steroids) or Serum Tears, (3) Withdrawal of the use of study drug (if worsening occurs during the course of the study). The decision will be made by the physician (Principal Investigator) based upon his clinical judgment as per the individual subject's clinical condition. If contact lens wear is instituted during the course of the study and/or the study drug is withdrawn, the subject will be withdrawn from the study. After any clinical worsening is noted, the subjects will be followed more closely (weekly) until complete resolution of symptoms and return to the subject's previous baseline. Subjects will be withdrawn from the study for presumed ocular allergic reaction to the product and ocular infection. The study will be stopped if the incidences of presumed ocular allergic reaction to the product and ocular infection surpasses 20% for each.

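### Sections 8.1, 3.5.2, 5.6 and 5.7 are inconsistent on whether worsening of existing dry eye disease is an adverse event, so the content of the adverse event rate by arm is unsettled

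*Combined protocol and SAP*

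**What the plan says.** Section 8.1 opens broadly: "An AE is any unfavorable and unintended sign, symptom, or disease temporally associated with the use of an investigational medicinal product (IMP". An inclusive list follows. One item covers events not seen before and, for the study disease, refers to "signs or symptoms associated with Dry Eye Disease (DED) that were not present prior to the AE reporting period". Another covers worsening: "Preexisting medical conditions (other than the condition being studied) judged by the investigator to have worsened in severity or frequency". Aggravation of DED that a subject already had is named in neither item.

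Section 3.5.2 has its own recording rule: "Clinically significant changes from baseline examination will be recorded on the adverse event forms". It makes no exception for DED, and the examination covers DED signs such as punctate keratopathy, filaments and mucoid films. Redness is included too: "Conjunctival hyperemia (ocular surface redness) will be graded at each visit using the VBR grading system". Section 1.4 ties these findings to the disease: "Common signs and symptoms of DED include: eye redness, ocular pain, burning and stinging sensation, foreign body sensation".

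Section 5.6 states: "Any worsening of DED or any adverse event due to the study drug will be recorded". It adds: "After any clinical worsening is noted, the subjects will be followed more closely (weekly) until complete resolution of symptoms". Section 5.7 has a similar recording sentence and mentions follow-up to resolution for adverse events only. Neither section says whether worsening of DED is itself an adverse event.

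Section 3.5 lists reported adverse events (Day 1 to Day 70) as a safety endpoint, and clinically significant examination changes as a separate one. Section 7.2 reports the adverse event/SAE rate by arm with a 95% confidence interval.

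**The concern.** Safety and tolerability form the primary objective (Section 2), and Section 1.7 says IVIG has not been given as eye drops before. Under inclusion criterion 4, every subject enters with at least six months of dry eye symptoms. Irritation caused by a drop can look like the burning, stinging or foreign body sensation that these subjects already report. The class of event left unsettled is therefore one in which local effects of the product could appear.

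As written, two events of the same kind may be handled differently. Clinically significant worsening of redness goes on the adverse event form under Section 3.5.2. Worsening of burning is an adverse event or not according to how Section 8.1 is read. The rate by arm could then include aggravated signs and leave out aggravated symptoms, and two staff members could classify the same case differently.

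**Working it through.** **1. The sections side by side, for events after the first dose.**

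| Event | 8.1 list | 8.1 general sentence | 3.5.2 | 5.6 and 5.7 |
|---|---|---|---|---|
| New DED sign or symptom | Named | Covered | Sign: on the form if clinically significant | Not classified |
| Existing redness, clinically significant worsening | Not named | Could be covered | On the form | Recorded, class not stated |
| Existing burning, worse | Not named | Could be covered | No rule for symptoms | Recorded, class not stated |

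The first row is clear. In the second, Section 3.5.2 places on the form an event that the Section 8.1 list omits. In the third, nothing settles the class.

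**2. Denominators.** Section 7.1 gives 12 per arm and a 10% attrition allowance. 12 / (1 − 0.10) = 13.3, rounded up to 14 per arm, or 28 in total, which reproduces the plan's figure. Section 3.1 uses 14 per group; the synopsis uses 12. Both are carried below, with equal arms as the plan states.

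**3. Shift per reclassified subject.** I read the rate as the proportion of subjects with at least one adverse event, which Section 7.2 does not spell out. On that reading a subject changes the rate only if he or she has no other adverse event:
- n = 14: 1/14 = 7.1 points
- n = 12: 1/12 = 8.3 points

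**4. Smallest case: no other events in the arm.** Section 7.2 does not name an interval method, so exact (Clopper-Pearson) two-sided 95% limits are used. For 0/n the upper limit is 1 − 0.025^(1/n).

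| Count | Rate | Exact 95% CI |
|---|---|---|
| 0/14 | 0% | 0% to 23.2% |
| 1/14 | 7.1% | 0.2% to 33.9% |
| 0/12 | 0% | 0% to 26.5% |
| 1/12 | 8.3% | 0.2% to 38.5% |

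**5. A range, by assumption.** The documents give no expected number of subjects with aggravated symptoms alone. If it were 1 to 4 in an arm, the shift would be at most 1/14 to 4/14 = 7.1 to 28.6 points, or 1/12 to 4/12 = 8.3 to 33.3 points. These are upper bounds, because any such subject with another adverse event is already counted.

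**The case against.** The strongest reply is that there is no outright contradiction. The Section 8.1 list is introduced as inclusive, and the general sentence before it is wide enough to cover worsened DED. Read that way, Sections 8.1 and 3.5.2 agree. Section 3.5.2 also says where a finding is written down, not what counts in a rate. This stands in part: the exclusion is an implication, and a reader who infers that the protocol bars worsened DED from being an adverse event goes further than the text. But the carve-out for the study disease has little purpose if such worsening counts anyway, so the opposite reading is also reasonable.

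A reader might also infer that aggravated symptoms or signs go unseen. The documents do not support that. Diaries collect adverse symptoms and are reviewed at Weeks 4, 8 and 10. Section 8.1 also provides for events found by questioning, and Section 5.6 requires weekly follow-up after clinical worsening. The tolerance VAS (the primary tolerability endpoint), OSDI, symptom intensity and SGA measure symptoms in both arms. Aggravated signs appear under the separate examination endpoint of Section 3.5, even if Section 8.1 is applied strictly.

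Nor do the documents support a claim of bias toward IVIG. The same text governs both arms, and the investigator and staff are masked. The rate is descriptive, and the stopping rule in Section 5.6 rests on presumed ocular allergic reaction and ocular infection, not on the overall adverse event rate.

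Finally, a shift of 1/14 or 1/12 follows from reclassifying any subject for any reason. That is true: the figures show how sensitive a small arm is, not how often this will occur.

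**Conclusion.** The point holds as an inconsistency of classification, and it should be corrected. The four sections do not give one answer on worsening of existing DED, and signs have a recording rule that symptoms lack. The consequence is an adverse event rate by arm whose content is not fixed and which may understate local effects. The size is up to 7.1 points (14 per arm) or 8.3 points (12 per arm) for each reclassified subject.

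This rests on three assumptions: equal arms, a rate counted per subject, and no other adverse event in the subject concerned. How many subjects would be affected cannot be derived from the documents. The point does not extend to the tolerability endpoint, the exploratory symptom measures or the stopping rule.

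**What to change.** Reconcile Sections 8.1, 3.5.2, 5.6 and 5.7 with one recording rule. Clinically significant worsening from Day 1 pre-dose is treated alike for DED signs and DED symptoms, and is entered on the adverse event form with a flag marking it as DED worsening. Tabulate flagged events by arm on their own line. In Section 7.2, report the overall adverse event rate by arm with and without them, so that the result no longer depends on which reading of Section 8.1 is preferred. Settle this before treatment codes are opened.

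The change is not purely one of reporting. Adverse event status is tied to the follow-up wording in Section 5.7 and to the possible replacement of withdrawn subjects in Section 8.1. The text should state that the flag does not by itself alter clinical management, and the sponsor should reconcile how flagged events relate to those two provisions.

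The cost is wording in four sections, a sentence in Section 7.2, one field on the form and one table line. More ocular events will be listed in both arms; the separate line and the saline arm make that background visible. Whether a worsening is clinically significant remains the investigator's masked judgement.

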Possible contamination of IVIG with infectious agents like viruses and prions always exists. However, viral inactivation steps, caprylation, and nanofiltration aid in the safety profile of IVIG.

2 Study Objectives

The main objective of this study is to establish whether patients with Dry Eye Disease are able to safely tolerate receiving Intravenous Immunoglobulin (IVIG) eye drops two times a day for eight weeks (primary 'safety and tolerability' objective). The exploratory objective is to investigate the preliminary efficacy of the use of IVIG eye drops in treating Dry Eye Disease (exploratory efficacy objective) to estimate the effectiveness of the trial intervention and collecting data to inform the design of a future definitive trial.

3 Study Design

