3.1 General Design

This will be a Randomized controlled trial, in which a total of 28 subjects will be enrolled at 1 clinical site. Subjects will be randomly assigned to one of two groups (#1, #2), with 14 subjects per group. One group will be given placebo (Normal saline eye drops) and the other group will be given eye drops containing the study drug (IVIG).

Patients with established Dry Eye Disease will be approached by a member of the research staff to determine if he/ she might be interested in participating in a research study. If the subject is interested, the research staff member will describe the study. If the subject is willing to enter the study, the study will be discussed and the subject will be asked to sign the informed consent form. Consent will be obtained prior to screening to determine eligibility. Screening procedures include documentation of Dry Eye Disease. Eligible subjects will be enrolled in the study.

All enrolled subjects will receive their first dose of test medication (placebo/ study drug) on study Day 1 in the doctor's office, and after completion of the study assessments, will have the topical eye drops dispensed for self-administration. See Section 5.4 *Preparation and Administration of Study Drug* for details.

Subjects will be provided with diaries to record the time of each dose and will also be asked to record any adverse symptoms. In addition, they will be asked to make a note of any missed doses together with the reason for the omission. Subjects will return at 4 weeks for further study assessments,

thereafter at 8 weeks (the last day of treatment), and again at 10 weeks after two weeks of no treatment with study drug for the final study assessments.

There is no primary efficacy endpoint in this study. Instead several exploratory efficacy endpoints will be assessed.

The primary tolerability endpoint is the change in the test substance tolerance between Day 1 (post-dose) and 8 weeks (56 days).

[figure not shown]

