5.3 Method for Assigning Subjects to Treatment Groups

This Randomized placebo-controlled trial will have two study groups. Subjects will be randomly assigned to one of two groups (#1, #2). One group will receive the study drug (IVIg 4mg/ml; test group), and the other group will receive placebo (Normal saline; control group). We will use a computer-based random code generator (Research Randomizer; <http://randomizer.org/>) to generate 1 set of 24 non-unique, unsorted numbers with a range from 1 to 2 representing the group number (#1/ #2). Each subject will be assigned a study identification (ID) number at screening, e.g. Subject #1, subject #2, and subject #3 and so on. Based on the randomizer generated table, subject #1 will receive either placebo or study drug. This will be repeated for each subject. For reproducibility purpose, we will document the final randomization schedule and the random SEED number used to generate the schedule. Randomization will be performed by the Illinois Eye and Ear Infirmary's pharmacy, and neither participants nor research staff will be aware of the assigned treatments. The person conducting the randomization will remain masked as well.

The study identification (ID) number will be used on all study-related documents. The drug vial number will be linked to the subject identification number.

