7.1 Sample Size Determination

As this is a feasibility trial intended to guide the planning of larger future investigations, there are no formal sample size calculations.⁶⁵ The aim of the study is to recruit a sufficient number of patients to evaluate the acceptability and safety of the intervention and the study design. An outcome of this study will be to estimate parameters such as the SD for a sample size calculation of a subsequent full-scale trial. A sample of 24 patients (12 in each arm) is considered adequate for obtaining reliable sample size estimates.^{66, 67} To allow for a conservative attrition rate of 10%, we aim to recruit 28 patients into the trial.

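### Replacing only adverse-event withdrawals makes enrolment depend on the outcome of a tolerability trial; the bias in the rates is small, but the 20% stopping rule's denominator can grow

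*Combined protocol and SAP*

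**What the plan says.** The only replacement provision is one sentence in 8.1: "Subjects who withdraw due to an adverse event may be replaced". It gives no maximum number, no arm for the replacement, and no rule for how the replaced subject counts.

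The related provisions are:

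- **Objective (section 2).** The main aim is "to establish whether patients with Dry Eye Disease are able to safely tolerate receiving Intravenous Immunoglobulin (IVIG) eye drops".
- **Sample size (7.1).** The plan says "there are no formal sample size calculations". It then says "A sample of 24 patients (12 in each arm) is considered adequate for obtaining reliable sample size estimates", and adds: "To allow for a conservative attrition rate of 10%, we aim to recruit 28 patients into the trial". Section 3.1 plans the 28 "with 14 subjects per group".
- **Allocation (5.3).** The pharmacy uses a random code generator "to generate 1 set of 24 non-unique, unsorted numbers with a range from 1 to 2 representing the group number". No entries beyond these 24 are described.
- **Forced withdrawal (5.6).** "Subjects will be withdrawn from the study for presumed ocular allergic reaction to the product and ocular infection". The next sentence stops the study if the incidence of either event passes 20%. It does not name the denominator.
- **Analysis (7.2, 7.3).** Rates are reported by arm with 95% confidence intervals. The intention-to-treat set keeps everyone randomised, whether or not they withdraw. Section 8.5 evaluates all exposed subjects for adverse events.
- **Retention (3.5).** The denominator is described as subjects eligible at Day 56, which does not settle whether earlier withdrawals are included.

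**The concern.** Replacement is triggered by the event being measured. A subject lost for any other reason is not replaced; one lost to an adverse event may be. An arm with more adverse-event withdrawals can therefore gain more subjects, and those additions enlarge the denominator of the rate that prompted them.

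Three quantities are exposed: the adverse-event withdrawal rate, the retention rate, and the incidence compared with 20% in 5.6. The third matters most in practice, because presumed ocular allergy and ocular infection both force withdrawal (so the subject becomes replaceable) and count toward stopping.

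The provision also adds a second allowance for attrition on top of 7.1, and needs an allocation step that 5.3 does not describe.

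**Working it through.** **1. The plan's own figure.** Inputs: 12 per arm and 10% attrition (7.1). 12/(1 − 0.10) = 13.3, rounded up to 14 per arm; 2 × 14 = 28. The stated target is reproduced. The allowance is 28 − 24 = 4 subjects, or 4/28 = 14.3%. The randomisation list has 24 entries, 4 short of the planned 28 before any replacement.

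**2. One realised trial.** Take an arm of 14 (3.1) with k adverse-event withdrawals (assumed). Suppose all are replaced in the same arm, no replacement withdraws, there are no other losses, and everyone stays in the denominator. The withdrawal rate moves from k/14 to k/(14 + k).

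| k | Withdrawal, no replacement | Withdrawal, with replacement | Retention, no replacement | Retention, with replacement |
|---|---|---|---|---|
| 1 | 7.1% | 6.7% | 92.9% | 93.3% |
| 2 | 14.3% | 12.5% | 85.7% | 87.5% |
| 3 | 21.4% | 17.6% | 78.6% | 82.4% |
| 4 | 28.6% | 22.2% | 71.4% | 77.8% |

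For k = 3 the exact 95% interval is 4.7% to 50.8% on 3/14 and 3.8% to 43.4% on 3/17.

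This table is a favourable case. If the three replacements carry a risk of 3/14 each, they add 3 × 3/14 = 0.64 expected withdrawals, and (3 + 0.64)/17 = 21.4%, which is no shift.

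**3. Expected bias.** Let X be the withdrawals among the first 14, binomial with risk p, and give the X same-arm replacements the same risk. Given X, the expected observed rate is X(1 + p)/(14 + X). This curve is concave in X, so its average lies below p: first cohorts with many withdrawals are diluted most. Averaging over X:

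| True risk p (assumed) | One round of replacement | Bias (points) | Replacing until 14 complete | Bias (points) |
|---|---|---|---|---|
| 5% | 4.71% | −0.29 | 4.68% | −0.32 |
| 10% | 9.49% | −0.51 | 9.39% | −0.61 |
| 20% | 19.22% | −0.78 | 18.91% | −1.09 |
| 30% | 29.11% | −0.89 | 28.54% | −1.46 |

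If adverse events are the only reason for leaving, retention is biased upward by the same amounts.

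**4. The 20% rule.** Assume incidence is taken over all subjects enrolled, that all 28 are enrolled, and that six have the same qualifying event.

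- Without replacement: the fifth event gives 5/28 = 17.9%, and the sixth gives 6/28 = 21.4%, above 20%.
- With the first five cases replaced by subjects who stay event-free: the denominator is 28 + 5 = 33, and the sixth event gives 6/33 = 18.2%, below 20%.
- If the sixth is replaced too, a seventh event gives 7/34 = 20.6%. In this example the threshold is passed one event later.

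**The case against.** The strongest reply is that the analysis sets already protect the rates. Intention-to-treat keeps every randomised subject, and all exposed subjects are evaluated for adverse events, so a withdrawn subject is not erased. Replacements meet the same entry criteria and are not chosen for tolerating the drops. The expected bias is below one point for one round, against intervals tens of points wide. The primary tolerability endpoint is the change in the tolerance scale (3.1), not a withdrawal rate, and 4.4.2 asks early leavers to complete that scale. A discretionary replacement could also serve as a backstop if losses exceed the allowance. All of this stands, and it limits the size of the point.

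It also rules out stronger readings that a reader might infer:

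- **Week 8 results enriched with tolerators.** A completer summary contains only completers with or without replacement. Adding completers from the same population changes their number, not their expected mean.
- **Retention of 100%.** This needs replaced subjects to be dropped, which the intention-to-treat definition does not allow.
- **Refilling the affected arm.** No section says that a replacement joins the arm that lost a subject. Same-arm entry is an assumption of the arithmetic above.
- **Masking must be broken.** The pharmacy could take a further random allocation and keep the masking. The documents leave the mechanics unspecified; they do not make them impossible.

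The reply does not answer two things: the trigger for replacement is still the outcome under study, and the stopping rule and the Day 56 retention rate still lack a clear denominator.

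**Conclusion.** The concern holds as a small, avoidable flaw in design. Replacement triggered by adverse events biases the observed withdrawal rate down and retention up, by about 0.3 to 0.9 points for one round at risks of 5% to 30%. That assumes 14 per arm, same-arm replacement, equal risk and all randomised subjects counted. The fall from 21.4% to 17.6% occurs only if all three replacements tolerate the drops.

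The more practical consequence is for the 20% rule, where the sixth event can read 18.2% instead of 21.4%. Those counts are illustrative and assume event-free replacements and a denominator of all enrolled subjects; the mechanism follows from the text of 5.6 and 8.1. The documents do not support a claim that tolerability failures would vanish from the results.

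**What to change.** Replace the sentence in 8.1 with: *Randomised subjects who have received study medication (IVIG or placebo drops) will not be replaced; the target of 28 already allows for attrition.* Naming both arms matters, because 5.1 uses the term study drug for IVIG alone.

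Add to 7.3 that all randomised subjects stay in the denominators of the adverse-event, withdrawal and retention rates, and reword the Day 56 rate in 3.5 to match. Section 5.6 should also state which denominator its 20% incidence uses; I propose no change to the rule itself.

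The cost is a few sentences and possibly slightly fewer than 24 completers if losses exceed the allowance of 4. That is a modest price in a trial with no formal sample size calculation. The change also removes an enrolment step for which the 24-entry list makes no provision.
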